This proposed study looks at the feasibility and acceptability of using clitoral vibration therapy, alongside current therapy, for women with vaginismus. It is likely that many, if not most, of these women will also have an element of vulvodynia. We propose that the use of external clitoral or vulval vibration therapy is likely to be acceptable in most women with vaginismus, based on acceptability of vulvar vibration therapy in women with vulvodynia. We propose based on the evidence above that vibrator therapy may help women with female sexual dysfunction to use vaginal dilators, based on study showing improvements with sexual distress and satisfaction.

Enrollment

This is a nonrandomized controlled trial, with the initial cluster of patients receiving standard therapy, and the second cluster receiving standard therapy plus vibrator. We aim to recruit an initial 15 participants who will receive standard therapy, and another 15 who will receive an external vibrator.

We expect this to take place over approximately 24-48 months. Enrollment of patients will be from a joint psychosexual clinic led by a medical doctor and a clinical psychologist. Female patients are referred to this clinic by General Practitioners, from within the Sexual Health service, or via Gynaecologists, frequently with complaint of difficulty or pain with penetrative sex. Inclusion and exclusion criteria have already been outlined.

Trial information will be given at the initial appointment. If the patient wishes to enrol, then an initial baseline questionnaire will be given, and a follow up questionnaire will be filled out by phone contact at 6-24 months afterward the initial consultation at the patients consent.

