6.2 Secondary objective

Does the use of clitoral/ vulval vibrators help women to progress more easily with the use of vaginal dilators compared to women not using these? Is there any self-reported difference in experiences of pleasure or enjoyment around sexual experiences in the two groups of women as reported by FSDS and FISI Scores? Do more women report enjoyable sex? Are there any differences noted in reported ability to have or enjoyment of penetrative sexual intercourse?

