The follow up questionnaires will be filled out by phone contact 6-24 months after the initial consultation at the patients consent if they agree to remain enrolled in the trial for both group 1 and group 2. This will take approximately 30 mins and will be arranged at a time convenient for the patient. This interview will be carried out by a doctor. Answers will be recorded directly onto the follow up questionnaire proforma.

4 point Likert scale 1 (Strongly disagree) to 4 (Strongly agree)

9. Study procedures

- Informed consent – verbal and written will be given, patients will be offered opportunity to enrol on the day (for convenience) or to return at another point to enrol.
- Screening and recruitment – as outlined previously recruitment will be directly from clinic
- Randomization – this is a non-randomized controlled trial, as trial participants need to be identified as time goes on, and a certain number of control and intervention participants are needed. The initial 10-15 recruited will receive standard treatment, and then the next 15 will receive intervention.

Study interventions

Study intervention	Contact (Visit) 1	Contact 2		
Medical history	X			
Consent	X			
Baseline Questionnaires (FSDS, FSFI, custom questionnaire)	X			
Phone Interview (FSDS, FSFI, custom questionnaire)		X		

Vaginal dilators will be provided to both groups (if available) and external genital vibrators to the second (intervention) group.

- Concomitant medications – per standard treatment, patients with vulvodynia may be prescribed topical lidocaine gel and may also receive nortriptyline if there is unprovoked vulvodynia present.
- Criteria for discontinuation – if patients withdraw consent for being enrolled in the study then follow up will discontinue.
- Procedure for collecting data, including Case Report Forms (CRFs) and storage: CRFs will be filled out electronically, and stored in a password protected file. The research data will be archived for 25 years according to Queen Mary University of London/ Barts Health NHS Trust policy, JRMP SOP 20.

- Follow up will be via phone interview. Patients enrolled will receive a contact email address in case of queries in the meantime during research period.
- End of study duration will be at follow up questionnaire (at 6-24 months post initial appointment and questionnaire)

10. Assessment and management of risk

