11.1 Sample size

Pilot / Feasibility study

30

This is a realistic number we can expect to recruit (15-20 in each study arm) over the course of 24-48months as a feasibility study.

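### The stated reason for not randomising is not valid, and enrolling all controls before all vibrator women leaves the causal question in section 6.2 unanswerable without untestable assumptions

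*Protocol*

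**What the plan says.** Section 9 (Randomization) gives two reasons for the design. The first reads: "this is a non-randomized controlled trial, as trial participants need to be identified as time goes on". The second is that each group must reach a set size. The section then fixes the order of allocation: "The initial 10-15 recruited will receive standard treatment, and then the next 15 will receive intervention".

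Section 5 (Enrollment) describes the same scheme, "with the initial cluster of patients receiving standard therapy, and the second cluster receiving standard therapy plus vibrator", with the numbers "We aim to recruit an initial 15 participants who will receive standard therapy, and another 15 who will receive an external vibrator". Section 8 also places Group 1 first and Group 2 next. Section 11.1 expects recruitment "over the course of 24-48months as a feasibility study", and the synopsis limits the whole study to 48 months.

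Among the secondary objectives, section 6.2 asks whether vibrators "help women to progress more easily with the use of vaginal dilators compared to women not using these". It also asks whether enjoyment and intercourse differ between the groups. The synopsis repeats these questions. The primary objective (6.1) is the acceptability of vibration therapy. Section 22 lists, as an intended use of the results, backing for recommending the therapy.

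**The concern.** Neither stated reason prevents randomisation. Trials routinely randomise patients as they present, and blocking exists to deliver planned group sizes. The protocol offers no other reason, such as contamination or device supply.

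The sequential rule has a cost. No control is recruited alongside any vibrator woman, so anything that changes over the recruitment years falls wholly on the group contrast. The protocol itself leaves several things free to vary:

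- the mix of lidocaine gel, tricyclics and physiotherapy (section 8);
- dilator supply, which depends on availability (section 9);
- the interviewer (section 7 allows medical students, section 8 names a doctor);
- the timing of follow-up, anywhere from 6 to 24 months.

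If the study closes on one common date, the women with least possible follow-up will all be vibrator women.

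Because assignment depends only on enrolment order, recruiting clinicians also know the current assignment before they seek consent. In the second phase they are recruiting to a group that receives a device to keep (section 12), so the two phases may enrol different women.

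At stake is the one causal sentence in 6.2, and whether results can carry the use that section 22 gives them.

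**Working it through.** **The plan's own figure.** The total is 30. Section 5 gives 15 + 15 = 30, which agrees. Section 8 (10-15 per group) gives 20-30. Section 9 (10-15, then 15) gives 25-30. Section 11.1 (15-20 per arm) gives 30-40, so only its lower end agrees. These should be reconciled, but the present point does not depend on it. No alpha, power, effect size or SD is stated, so there is no power calculation to reproduce.

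**Do the two reasons hold?** Permuted-block lists for 30 consecutive women were simulated 20,000 times (seven blocks of 4 and one of 2). Every list gave exactly 15 and 15. The mean absolute correlation of group with enrolment order was about 0.02, and the largest variance inflation was 1.01. Consecutive arrival and fixed numbers are both compatible with randomisation.

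**Can group and period be separated under the sequential rule?** Take 15 controls, then 15 vibrator women.

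- With columns for intercept, group and period (first or second half of enrolment), the design matrix has rank 2 of 3. The group and period effects cannot be estimated separately.
- If drift is instead assumed exactly linear in enrolment order, the correlation of group with order is r = 0.8665. Variance inflation is 1/(1 − r²) = 1/(1 − 0.751) ≈ 4.0. Separation is then possible, but only under a form of drift that the data cannot test.

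**Gap in enrolment dates.** Assume even accrual over T months, with a fraction p enrolled first as controls. Mean dates are pT/2 for controls and (1 + p)T/2 for vibrator women. The difference is T/2 for any p, so 10 then 15 gives the same gap as 15 then 15.

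- T = 24: the gap is 12 months.
- If the 48-month study limit includes the minimum 6-month follow-up, T is at most 48 − 6 = 42 and the gap at most 21 months.

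**Illustration of bias.** The drifts below are assumptions, not figures from the protocol. A linear drift of D SD over 30 women shifts the group difference by D × 15/29. With SE = √(2/15) = 0.365 SD and a nominal two-sided 5% z-test:

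| Drift D (SD) | Spurious difference (SD) | False-positive rate |
|---|---|---|
| 0.25 | 0.13 | 6% |
| 0.5 | 0.26 | 11% |
| 1.0 | 0.52 | 29% |

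No such test is planned. The middle column is the relevant one, because a side-by-side description would show the same shift.

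**What randomising would not cure.** At 15 per group the detectable difference is (1.960 + 0.842) × 0.365 ≈ 1.02 SD (80% power, two-sided 5%, both assumed).

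**The case against.** The strongest reply is that this is an openly non-randomised acceptability study. Section 13 says it aims only at feasibility and acceptability, section 5.3 leaves efficacy to later work, and section 11.2 says statistical analysis will not be relevant at these numbers. The primary objective does not depend on allocation, and randomising 30 women would still leave a very imprecise comparison. All of this stands, and it limits the weight of the point. It does not make the section 9 rationale valid, and it leaves a causal question in 6.2 that the design cannot support.

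Several stronger readings are tempting but not supported:

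- *All of 6.2 is unanswerable.* Only the dilator sentence asks about help. The others ask whether differences are reported, and two non-randomised groups can be described.
- *No analysis could ever separate the effects.* An assumed form of drift would allow it. Baseline characteristics (5.2) and questionnaires at both contacts can also show some differences in who joined and give within-woman change. They do not remove period effects.
- *Women know their group before consenting, or each phase is told something different.* The consent material is not shown. Staff foreknowledge follows from the enrolment rule; what women are told does not.
- *Standard care is known to change over time.* The variable mix in section 8 may simply reflect tailoring to the patient, and psychotherapy is stated separately from it. Change is possible but not documented.
- *The gap could reach 24 months.* That needs 48 months of recruitment, which does not fit a study of up to 48 months with at least 6 months of follow-up.

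The contamination argument also has force: concurrent groups would share a clinic, and vibrators are on open sale (section 10). It is a real downside of randomising, but the protocol does not give it as its reason.

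**Conclusion.** The point holds in a limited form. Both reasons in section 9 fail. Group is fully mixed with calendar period, and recruiting staff know the current assignment before consent. Whether vibrators help dilator progress compared with not using them cannot be answered without untestable assumptions about drift. The remaining 6.2 questions can be answered only as descriptions, and the acceptability objective is untouched.

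The size is a gap in mean enrolment dates of 12 to about 21 months, with no overlap between groups. It rests on even accrual and, at the upper end, on the 48-month limit including follow-up. It is a gap in time, not an estimate of bias in any outcome; the protocol gives no figure from which that bias could be estimated.

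**What to change.** **Preferred.** Replace the sequential rule in sections 5, 8 and 9 with 1:1 allocation from a permuted-block list of varying block size. Conceal it in sealed opaque envelopes prepared by someone who does not recruit, and open each only after consent and the baseline questionnaires. If the leaflet currently differs by phase, use one that describes both groups. This costs a protocol amendment, possibly a leaflet amendment, and a person outside the recruiting team to prepare the list. It needs no extra patients or visits. The downside is contamination, since control women may obtain a vibrator themselves; follow-up should ask about this. Fifteen per group stays imprecise, and the protocol should say so.

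**If the sequential scheme is kept or has already begun.** Delete the rationale in section 9. Reword 6.2 and the synopsis objectives as a side-by-side description of the two groups with no effect claim. State calendar period and selection into each phase as limitations. Change section 22 so that it no longer says the results will support a recommendation. This costs almost nothing beyond an amendment.

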6.4 Secondary endpoint

Baseline and follow up questionnaires will be used specific to study and also FSDS and FISI.

7. Study population

Potential participants will be identified from the patients presenting to the Female Sexual Wellbeing Clinic. Identification of participants beyond this will not be needed. The identification of suitable participants will be done by the clinicians, using the inclusion and exclusion criteria taken into account. The clinic is a joint clinic run by a clinical psychologist and medical doctor, who will be providing the initial

questionnaire and the follow up phone interview. Medical students (with honorary contract obtained) may also carry out interviews but not consent for the study.

Potential participants will be advised of the study verbally and given a written leaflet during their clinic appointment. Enrolment will be offered on the day on the understanding that the patient can decide to leave the study at any point.

Informed consent will be obtained. Consent will be taken by either the medical doctor or clinical psychologist in clinic. Verbal explanation of the study, together with a leaflet explaining the study will be provided.

If the study participants wish to enrol on the day, they will be able to. This may be preferable for convenience to avoid having to return to the clinic. Otherwise they will have 24hrs - 1 week to enrol. Enrolling on the day may be a preferred option for the patient so they do not have to return to clinic again. If they wish, they can take the written information away with them and return on another day.

Participants will enrol for approximately 6-24 months; this will be from the initial consultation until the follow up questionnaire, although no contact in the interim will be required as part of the research project there may be contact as part of any medical or psychological intervention separate to the project.

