Patients the Female Sexual Wellbeing clinic sometimes find discussions embarrassing as we discuss sexual difficulties. This is not confined to patients in the study. We aim to minimise embarrassment and difficulties discussing sensitive topics by providing a questionnaire at baseline, and a follow up phone call rather than face to face interview is also likely to help reduce embarrassment. If the pilot study suggests that patients would prefer a different form of communication then this will feed into any further research. Financial loss for participants is not expected.

The clitoral vibrators supplied to the patients in the intervention group are already available for sale to people in the UK. No published long term side effects from the use of these are known or foreseen.

Rubin et al published a clinical reference guide on sexual devices for clinicians in 2019 which stated that risks associated with sexual devices (such as vibrators) were traumatic injury or infection. Since we are recommending use of the vibrator for external use only, barrier use over sexual devices if shared, and proper disinfection to reduce risk of infection (Rubin, 2019).

In the unexpected case of an SAE this will be reported via the appropriate routes and the study management group will decide on whether the study should proceed or not. Participants will have an email address to contact the CI in case of AE or SAE.

No risks to researchers foreseen.

11. Statistical considerations

Qualitative study N/a

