16.5 Other biological or chemical products

N/a

17. Safety reporting

Adverse Events (AEs) and Adverse Reactions (ARs) will be recorded. Serious Adverse Events (SAEs) and Serious Adverse Reactions (SARs) will be reported to the CI as medical assessor for the sponsor and coordinating team. All unexpected SARs (SUSARs) will be reported to the JRMO and REC.

DEVICE DEFECTS, RECALLS and ALERTS

The intervention is an external vibrator which is available for sale in the UK. It is not a medical device.

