17.1 Adverse Events (AEs)

An AE is any untoward medical occurrence in a participant to whom an intervention has been administered, including occurrences which are not necessarily caused by or related to that intervention. An AE can therefore be any unfavourable or unintended sign (including an abnormal laboratory finding), symptom or disease temporally associated with study activities.

In a study of the effects of genital vibration therapy in women with arousal and orgasm disorders, light-headedness, agitation, headache, facial flushing, were each reported by 4-8% of participants, with 2% reporting some genital numbness, dizziness or cramping (Guess, 2008).

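### The protocol promises to record adverse events, but the only participant reporting route it names is self-initiated email and it lists no enquiry at the single follow-up call, so mild events are likely to be missed

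*Protocol*

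**What the plan says.** Protocol section 17 opens with a commitment: "Adverse Events (AEs) and Adverse Reactions (ARs) will be recorded". Section 17.3 adds that a non-serious event is documented and the woman followed up. Section 19 calls a management-group meeting if any adverse event arises.

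On how an event reaches the study, section 10 says: "Participants will have an email address to contact the CI in case of AE or SAE". Section 9 describes what appears to be the same facility more loosely: "Patients enrolled will receive a contact email address in case of queries in the meantime during research period".

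The schedule has two contacts. Section 7 states that "no contact in the interim will be required as part of the research project", and continues that "there may be contact as part of any medical or psychological intervention separate to the project". The second contact is one phone interview at 6-24 months, in both groups. Its line in the section 9 table reads "Phone Interview (FSDS, FSFI, custom questionnaire" and closes there. The table has no adverse-event row. Section 18 rules out routine monitoring and points to the contact details given to patients. Section 14.2 restricts use of the medical records to diagnosis, treatments provided and age.

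Section 17.1 cites an earlier device study in which light-headedness, agitation, headache and facial flushing "were each reported by 4-8% of participants", with genital numbness, dizziness or cramping at 2%. Section 10 cites traumatic injury and infection as device risks.

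**The concern.** The commitment to record adverse events is not matched by any stated step at which someone asks about them. The protocol names the symptoms and risks it has in mind, then leaves the woman to start the report. A passing headache or short-lived numbness is unlikely to prompt an email to the chief investigator, and it may be forgotten by a call up to 24 months later. Sections 10 and 12 also say that patients in this clinic sometimes find discussion of sexual difficulties embarrassing.

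What is at stake is how a short or empty adverse-event list would be read. Section 22 expects the results to support recommending vibration therapy. Without a defined enquiry, a reader could not tell whether no events occurred or nobody asked. How adverse events are elicited is a study procedure and belongs in the protocol, so this is not a detail that a statistical analysis plan would be expected to supply.

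**Working it through.** The protocol states no figure for adverse-event capture, so there is none to reproduce. The check has two parts.

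**1. Possible routes, set side by side**

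| Possible route | What the protocol says | Does it make anyone ask? |
|---|---|---|
| Email to the chief investigator | Available to all enrolled women (sections 9, 10) | No; the woman must start it |
| Interim study contact | Not required (section 7) | No |
| Interim clinical contact | May occur, separate from the project (section 7) | No instruction to ask or to forward |
| Medical records | Consulted for diagnosis, treatments and age (14.2); a place to document a known event (17.3) | No |
| Routine monitoring | None (section 18) | No |
| Follow-up call | FSDS, FSFI, custom questionnaire (section 9) | Not listed; custom questionnaire not shown |

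Every route except the last is passive or is not directed at adverse events. The last is open only because the custom form cannot be seen.

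**2. Scale**

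Inputs:
- n = 15 women in the vibrator group (section 5, Enrollment).
- True rate p = 2%, 4% or 8% per symptom (section 17.1; the 2% is taken as applying to each symptom).
- Share of cases reported, s. The documents give no value, so s = 100%, 75%, 50% and 25% are shown. All but the first are assumptions about the shortfall.

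Expected cases with full capture, n × p: 15 × 0.02 = 0.3; 15 × 0.04 = 0.6; 15 × 0.08 = 1.2.

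Chance of at least one reported case = 1 − (1 − p·s)^n:

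| s | p = 2% | p = 4% | p = 8% |
|---|---|---|---|
| 100% | 1 − 0.98^15 = 26% | 1 − 0.96^15 = 46% | 1 − 0.92^15 = 71% |
| 75% | 20% | 37% | 61% |
| 50% | 1 − 0.99^15 = 14% | 1 − 0.98^15 = 26% | 1 − 0.96^15 = 46% |
| 25% | 7% | 14% | 26% |

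Sections 8 and 11.1 give other group sizes. With full capture, 10 women give 18%, 34% and 57%; 20 women give 33%, 56% and 81%.

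If no case is reported among 15 women, the one-sided 95% upper limit for the reported rate is 1 − 0.05^(1/15) = 18%. With full capture that is also the limit for the true rate. If only half of cases are reported, the same zero allows a true rate of up to 0.181 / 0.5 = 36%.

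The 100% row and the 18% limit reflect the small sample and would remain after any fix. The part due to passive reporting is the drop from that row to the lower rows, and the widening from 18% to 36%.

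**The case against.** The strongest reply is that the protocol does not make email exclusive. An interview of about 30 minutes takes place in both groups, and section 8 has a doctor conduct it. Standard treatment includes psychotherapy and may include physiotherapy, so clinic staff may hear of problems. Section 19 lets investigators as well as participants raise issues. The custom questionnaire is not shown and might contain an adverse-event item. The product is on general sale, there is no safety endpoint, and the cited rates come from women with arousal and orgasm disorders, whom section 5 calls a slightly different population. The capture shares have no source in the documents.

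Much of this stands. A reader might infer that events can reach the study only by email, or that under-counting is certain. The documents support neither; email is the only *named participant* route, and under-ascertainment is likely, not demonstrated. Sections 17.3 and 19 can still operate on any event that comes to light.

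A reader might also infer that the two groups are ascertained unevenly. That is not supported. The email address goes to all enrolled women, the same call applies to both groups, and no section sets different collection by group. The nearest thing is the definition in 17.1, tied to a participant who has been given an intervention, whose reach over the standard-treatment group is not stated. That is an ambiguity to close, not evidence of imbalance.

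The reply does not show a step at which anyone is required to ask. If the custom form does contain an item, the protocol should say so.

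**Conclusion.** The point holds in limited form. The protocol commits to recording adverse events, names only participant-initiated email as the reporting route, and lists no enquiry at its one follow-up contact. Mild and transient events are likely to be under-ascertained, so few or no reports would be weak evidence about harms.

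If half of cases are volunteered, the chance of seeing at least one case among 15 women falls from 26%, 46% and 71% to 14%, 26% and 46% at true rates of 2%, 4% and 8%. These figures assume that the cited rates carry over to this population and that women report independently of one another. The one-half share is purely illustrative. They show scale and do not predict the shortfall.

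The protocol should be changed because the remedy is cheap and uses a call that already takes place. No claim of uneven ascertainment between the groups should be attached to it.

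**What to change.** - Section 9 table: add an adverse-events row, marked at Contact 2.
- Follow-up proforma: add a fixed prompt covering the symptoms listed in 17.1, genital injury, irritation or infection, and one open question, asked in the same words in both groups. If the custom questionnaire already contains such an item, cite it in sections 9 and 17.
- Section 10: state that email is an additional route.
- Section 17.1: state that the adverse-event definition covers both groups.
- Reporting: give adverse events per group, with the number of women actually asked as denominator and the time since enrolment at the call. State recall over 6-24 months as a limitation, because a prompt at Contact 2 does not remove it.

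Cost: one table row, a short checklist and about two extra minutes per call. Reported rates will probably be slightly higher than under spontaneous reporting, and the write-up should say that events were prompted.
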